13 STATISTICAL ANALYSES

13.1 Primary analyses and Sample size

The primary endpoint of non-inferiority will be reached if the lower CI around the ratio of geometric mean concentration (GMC) of IgG (fractional/full dose) is ≥ 0.5 (i.e. the 2-fold criterion) at 1-month post-boost dose (10 months of age).

A secondary endpoint will assess the proportion of ‘responders’, defined as those with serotype-specific IgG antibody concentration ≥ 0.35 mcg/ml[13] at 4 weeks after the primary series (18 weeks of age). Non-inferiority will be achieved if the lower limit of the 95% confidence interval (CI) around the difference in the proportion of ‘responders’ (fractional dose group – full dose group) is $> -10\%$ [76] post-primary series (18 weeks of age) for at least 8 of the 10 vaccine types in the PCV10 arms and at least 10 of the 13 vaccine types in the PCV13 arms. Assessments of non-inferiority will be made separately for each of the vaccine type serotypes. Our primary endpoint will be reached across all arms if non-inferior immunogenicity is achieved for the 10 serotypes in PCV10 as this is the standard of care in Kenya currently.

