A co-primary analysis, which has a precedent in PCV licensure analyses[83], will determine whether the immune responses elicited by the fractional doses (20% and 40% doses) are non-inferior to the lowest serotype-specific immune response elicited by the full dose PCV, 4-weeks after the primary series. In PCV13 licensure analyses, the immunogenicity of new PCV13 serotypes, not included in PCV7, were assessed in non-inferiority comparisons with the lowest response observed among the PCV7 serotypes in PCV7 recipients, the response to serotype 6B, for which there was existing evidence of both efficacy and programmatic effectiveness[83]. In adapting this approach to our study, non-inferiority will be achieved if the lower limit of the 95% confidence interval (CI) around the difference in the proportion of 'responders' (fractional dose serotype 'x' – full dose 6B) is >-10%.

The timing of the primary endpoint, at 4 weeks after the booster dose, aligns with the aim to assess the effectiveness of the whole three dose schedule (rather than partial vaccination with 1 or 2 doses). It will give an indication of protection in the second year of life, this is clinically relevant as it is thought that the enhanced protection in the second year of life, as a result of a booster dose, has an important impact on carriage and transmission in toddlers, which may enhance herd protection, compared to a 3p+0 schedule[20]. In a 2p+1 schedule in Kenya, a smaller proportion of children may reach the protective threshold of antibodies after the 2 primary doses in early infancy, compared to after three primary doses, but in the context of low rates of disease after 6 years of PCV10 implementation, young infants would be protected by the indirect protection afforded by the reduced transmission of pneumococci. The timing of the endpoint corresponds to previous literature analysing 2p+1 schedules and is in line with standard practice to analyse non-inferiority trials in the ATP population.

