13.2 Secondary analyses

We will present the serotype-specific difference in proportions of children with evidence of vaccine serotype carriage by trial arm. In Kilifi, residual carriage of PCV10 serotypes under the routine immunisation schedule has been estimated in 2016 at 6%; assuming 300 per arm, we expect to estimate the combined prevalence of PCV10 serotypes in each arm with an accuracy of $\pm 2.7\%$. Carriage of the 3 additional PCV13 serotypes in children aged under 5

years in Kilifi in 2016 was 22%; assuming 300 per arm, we expect to estimate combined prevalence of PCV13 serotypes in each arm with an accuracy of $\pm 5.0\%$.

The indirect effect of the PCV10 programme, which has been implemented in Kenya for 6 years, has reduced the carriage prevalence of PCV10 serotypes in Kilifi to 6% among children <5 years; this limits the power to examine the direct effect of different doses of PCV13 on carriage of the serotypes contained in PCV10. However, the population impact of the PCV10 programme has also led to an increase in the carriage prevalence of the serotypes that are contained in PCV13 but not in PCV10 (3, 6A and 19A). We will use carriage of these serotypes in the PCV10 full dose arm as a control against which to test of the direct effect of the full and fractional doses of PCV13. The effectiveness of PCV13 against carriage of serotype 3 is limited^{22 67} so we will concentrate in this analysis on serotypes 6A and 19A; the combined carriage prevalence of these serotypes among children aged <5 years in Kilifi is 19%. Assuming this prevalence at 18 months of age among the children receiving full dose PCV10, 300 infants per arm would confer 92% power to detect a 50% reduction in carriage in any of the PCV13 arms (leading to a prevalence of 9.5%); and 78% power to detect a 40% reduction in any of the PCV13 arms (leading to a prevalence of 11%). These effect estimates would be in line with previous literature on the direct effect of PCV13 on carriage prevalence⁶⁴⁻⁶⁶. A total of 290-300 per arm at 18 months of age would confer just over 80% power to determine whether full and fractional dose arms exhibit non-inferior prevalence of PCV10 vaccine-type carriage using a non-inferiority margin of 5%.

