The results from the multiplex opsono-phagocytic assay (MOPA) to all vaccine serotypes plus 6C will be used to compare IgG functionality after 3 full doses of PCV10 or PCV13 with that after 3 fractional doses of PCV10 or PCV13 at 1-month post boost. Antibody function will also be compared between products for comparable schedules. The correlation between IgG concentration and functional activity following a third dose of PCV delivered in a 2+1 schedule will be assessed. Exploratory analyses will derive a functional correlate of protection against carriage using the post booster MOPA titre and vaccine type carriage at 18 months of age for serotypes 19A and 6A.

To evaluate the safety of the fractional dose delivery we will describe:

- the proportion of infants in each trial arm experiencing specified local vaccination site reactions (e.g. redness, swelling) within the 30 minutes immediately after vaccination as observed by study personnel;
- the proportion experiencing local/systemic adverse reactions, e.g. injection site abscess, in the 7 days after vaccination, as reported by mother or the legal guardian who accompanied the infant to the vaccination session at a day 8 visit.

We do not expect to have the statistical power to determine a difference in the risks of injection site abscess between arms as the risk of injection site abscess is expected to be low. Pentavalent vaccine delivered in 10-dose vials in Kenya resulted in 128 abscesses per 100,000 injections[84]. If this baseline level of risk applies to the 3 immunisations given to 1200

children in the fractional dose groups we would expect to see no more than 5 abscesses throughout the whole study.

The sera of all participants in the seventh trial arm (Arm G) will be assayed for immunogenicity to 7 serotypes (the PCV7 vaccine types) at 4-weeks post-primary series only. The proportion of responders in Arm G at 4-weeks post-primary series will be compared to that of the PCV10/13 2p+1 arms at 4-weeks post-primary series. Non-inferiority will be achieved if the lower limit of the 95% confidence interval (CI) around the difference in the proportion of 'responders' (2p+1 - 3p+0) is $>-10\%$ [76]. Assuming the proportion of children reaching the threshold antibody concentration across serotypes at 18 weeks of age is on average 87%[33], with 300 per arm, we would have 85% power to declare non-inferiority using a margin of 10%, accounting for 7 serotype-specific comparisons.

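### The 85% power stated for the arm G comparison does not follow from its 95% CI rule: the stated inputs give about 95% per serotype, or about 72% if all 7 independent serotypes must pass

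*Combined protocol and SAP*

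**What the plan says.** Section 13.2 (Secondary analyses) assays arm G sera for the 7 PCV7 serotypes at 4 weeks after the primary series and compares responder proportions with those of the 2p+1 arms. The decision rule reads "Non-inferiority will be achieved if the lower limit of the 95% confidence interval (CI) around the difference in the proportion"; the difference is in responders, 2p+1 minus 3p+0, and the limit must be greater than −10%. The next sentence assumes that on average 87% of children reach the threshold, takes 300 per arm, and concludes that "we would have 85% power to declare non-inferiority using a margin of 10%, accounting for 7 serotype-specific comparisons".

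The section does not say how many of the 7 serotypes must meet the criterion, what accounting for 7 comparisons means, or what correlation between serotypes was assumed.

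Section 13.1 (Primary analyses and Sample size) does give a pass count for its own responder endpoint, fractional against full dose: "for at least 8 of the 10 vaccine types in the PCV10 arms and at least 10 of the 13 vaccine types" for PCV13. It also says: "Assessments of non-inferiority will be made separately for each of the vaccine type serotypes". Neither statement is tied to the 7 serotypes of arm G.

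**The concern.** The rule and the power stand in adjacent sentences, so the power ought to follow from the rule. A 95% CI lower limit is a one-sided 2.5% test. Three of the four quantities needed (responder rate, number per arm, margin) are given and the CI level supplies the fourth, so the figure can be checked. The only freedom left is how the 7 serotypes combine.

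Section 9.2 explains that the 3p+0 arm is there to bridge the 2p+1 findings to Kenya's existing schedule. The stated power is what a reader has for judging how informative that bridge is. A failure to show non-inferiority reads differently if the chance of missing it is about 5% (one serotype judged alone), 15% (as the plan implies) or about 28% (all 7 required, under the conditions set out in the working). With no pass rule, success on this comparison could also be defined after the results are seen.

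**Working it through.** **Inputs, all from section 13.2.** Responder rate 87%; 300 per arm; margin 10 percentage points; 95% CI (one-sided α = 0.025); 7 serotypes; stated power 85%. The plan states no true difference, so I take it as zero, with 87% in both arms.

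**Formula.** Unpooled normal approximation for one serotype:

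power = Φ(0.10/SE − z), with SE = √(2 × 0.87 × 0.13/300) = 0.02746, so 0.10/SE = 3.642.

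**Reproducing the stated 85%.** At one-sided 5% (z = 1.645), power per serotype is Φ(1.997) = 0.9771. Requiring all 7, independent: 0.9771^7 = 0.850. This matches the plan exactly, but it corresponds to a 90% CI.

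**The written rule.** At one-sided 2.5% (z = 1.960), power per serotype is Φ(1.682) = 0.9537. With q = 0.9537 and independence:

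| Pass rule | Power |
|---|---|
| One serotype alone | 95.4% |
| All 7 (q^7) | 71.8% |
| At least 6 of 7 (q^7 + 7q^6(1 − q)) | 96.1% |
| At least 5 of 7 | 99.7% |

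No pass count gives 85%. The choice of interval does not explain the gap: exact enumeration at the 95% level gives 95.3% (Wald), 95.2% (Newcombe) and 95.0% (Farrington–Manning) per serotype, and 71.4%, 70.7% and 69.7% for all 7. Reaching 85% for all 7 independent serotypes under the 95% CI would take 355 per arm.

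**Adjusted level.** If accounting for 7 comparisons meant Bonferroni, one-sided α = 0.025/7 = 0.00357 (z = 2.690), and power for one serotype is Φ(3.642 − 2.690) = 82.9%. Šidák gives about 83%. Both are near 85% without equalling it, and both require a wider interval than the 95% CI in the rule.

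**Correlation, all 7 required, 95% CI.** With equicorrelated test statistics, power = ∫ φ(t) Φ((1.682 + √ρ t)/√(1 − ρ))^7 dt. The values of ρ are assumptions, since the documents give none:

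| ρ | All-7 power |
|---|---|
| 0 | 71.8% |
| 0.3 | 77.0% |
| 0.5 | 80.9% |
| 0.7 | 85.1% |

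A correlation of about 0.70 is needed for 85%.

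**What moves the 71.8% down.**
- *Loss.* Section 13.1 allows 5% loss at 4 weeks after the booster. Applied here, 300 × 0.95 = 285 per arm gives 94.4% per serotype and 0.944^7 = 66.8% for all 7.
- *Unequal serotypes.* The 87% is an average, and section 13.1 cites serotype-specific responses of 63–97%. Two assumed sets that average 87%, independent, 95% CI, 300 per arm:
  - 63, 85, 88, 90, 93, 95, 95%: powers 0.718, 0.929, 0.965, 0.983, 0.998, 1.000, 1.000; product 63%.
  - 75, 80, 85, 88, 92, 94, 95%: powers 0.807, 0.865, 0.929, 0.965, 0.995, 0.999, 1.000; product 62%.

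**The case against.** **85% is attainable under the written rule.** The 7 results come from the same infants' sera, so positive correlation is more natural than independence, and a test-statistic correlation near 0.7 gives 85% for all 7. This stands as a possibility, so the figure cannot be called impossible. But the plan states no correlation, whereas one-sided 5% with independence hits 85.0% with no extra assumption about serotypes.

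**An all-7 rule is written nowhere.** If the section 13.1 sentence on separate assessment is general, the relevant power is about 95% and the stated 85% is conservative. That is fair. It still leaves 85% unexplained, because judging each serotype alone at the 95% CI does not give it either. It also shows why the pass rule has to be stated.

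**Readings that go too far.** A reader might take 72% as the least the all-7 power could be, and 28% as the most the miss rate could be. The documents do not support this: the 72% needs exactly 87% in every serotype and 300 evaluable per arm, and section 13.1 itself cites a wide serotype range and 5% loss, both of which reduce it.

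A reader might also extend the point to carriage, where section 13.2 says that 290–300 per arm "would confer just over 80% power to determine whether full and fractional dose arms exhibit non-inferior prevalence of PCV10 vaccine-type carriage" with a 5% margin. At 6% prevalence that fits one-sided 5% (81–82%) better than a 95% CI (72–73%). However, the section gives neither a CI level nor an assumed prevalence for that power. Its 6% describes children under 5 in the community, and a 95% CI at about 4.75–5% prevalence gives roughly 79–82%. No error is shown there.

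**Conclusion.** The point holds as a minor inconsistency in a secondary analysis. The stated 85% does not follow from the written 95% CI rule and the stated inputs. Those inputs give about 95% per serotype. If all 7 serotypes must pass, they give about 72%, assuming independence, a true difference of zero, 87% in every serotype and no loss. The all-7 figure falls to about 67% with 285 per arm, falls further if serotype rates vary around 87%, and rises to 77–85% for assumed correlations of 0.3–0.7.

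The most likely source of the 85% is a one-sided 5% calculation with all 7 required. That is inferred from an exact numerical match, since the plan does not say so. A reader might conclude that the arm G comparison is underpowered; the documents do not show that, because they do not say which pass rule applies. Primary GMC power, type I error and enrolment are unaffected.

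**What to change.** In section 13.2:

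1. Keep the 95% CI and the 10% margin.
2. State whether the 7 serotypes are judged separately or whether all must pass. Section 13.3 says that a detailed SAP will be finalised before database lock; the same rule should be carried into it.
3. Replace the 85% with wording such as: *about 95% per serotype; about 72% for all 7, assuming independence, 87% in every serotype and 300 evaluable per arm (about 67% with 285 per arm; lower if serotype rates vary around 87%; higher if serotypes are positively correlated, for example 77–85% for assumed test-statistic correlations of 0.3–0.7).*

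The cost is wording only; enrolment, margin and CI rule do not change. The downside is that the all-7 power becomes less favourable than the figure now printed.

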Currently, two PCVs are available for introduction into the routine immunisation schedules of low- and middle-income countries (LMICs), Synflorix® (GlaxoSmithKline plc.) covers 10 pneumococcal serotypes and Prevnar 13® covers 13 serotypes (Pfizer Inc.). Although there is now evidence that immune correlates of protection for vaccine serotype-specific IgG responses may vary by serotype[2], both vaccines have been licensed based on the immune correlate of protection for vaccine serotype-specific IgG responses of 0.35 mcg/ml IgG established using PCV7[12, 13]. There is little evidence of cross-protection against non-vaccine pneumococcal serotypes[9, 12]. The World Health Organization (WHO) currently recommends PCV10 or PCV13 for use in routine immunisation programmes in a three dose schedule: in a primary series at 6, 10 and 14-20 weeks of age (the '3p+0' schedule), or two primary doses at 6-8 weeks and 14-16 weeks with a booster at least 6 months after the 2nd dose (e.g. 11-15 months of age; the '2p+1' schedule)[12]. In high income countries, where disease incidence generally peaks later in childhood than in LMICs[14], the 2p+1 schedule has demonstrated effective direct protection against carriage and IPD and additionally stimulates strong herd protection at the population level[11, 15, 16]. In most LMICs, including Kenya, rates of pneumococcal disease peak in the first 6 months of life, and uptake of vaccines scheduled for the second year of life is low, so a 3p+0 schedule has been adopted to ensure direct protection from disease as early in life as possible[14]. However, there is evidence that the IgG concentrations after 2 primary doses delivered with a 2 month interval are equivalent to those produced after 3 doses that are each 1 month apart[17, 18]. Additionally, data from Australia indicate that a 3p+0 schedule of PCV13 may have resulted in less substantial declines in IPD compared to those seen in the UK or USA, where 2+1 and 3+1 schedules have been used respectively[19]. As PCV programmes mature and evidence accrues, schedules in LMICs may also change to 2p+1 in order to take advantage of the potential additional benefits of herd protection[19-21]. This approach is supported by recent data from South Africa, a relatively high transmission setting, where a 2p+1 schedule of PCV7 has demonstrated a 48-60% reduction in carriage prevalence at 12 months of age compared to a PCV-unvaccinated historical cohort[22, 23]. IgG concentrations pre-boost were greater than 0.35 mcg/ml for all 7 vaccine types indicating that, importantly, direct protection may have been maintained in the period between the primary series and boost dose[24]. Persistence of high IgG concentrations could be due to the persistence of the vaccine-induced immune response and/or natural boosting through exposure to circulating

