8.3 Secondary objectives

- To determine the functionality of the immune response to full and fractional doses at the 1-month post-boost time point using an opsonophagocytic assay.
- To compare vaccine efficacy against carriage of non-PCV10 serotypes 6A and 19A in the full dose PCV13 arms when compared to the fractional dose arms, using the full dose PCV10 2p+1 arm as a control, with primary analyses at 18 months of age and secondary analyses at 9 months of age. The carriage prevalence of the common vaccine serotypes (PCV10 serotypes) in the fractional dose arms will also be compared against the carriage prevalence in the full dose arms.
- To compare frequency and severity of local injection-site reactions and vaccine-related adverse events in the 28 days following immunization after fractional dose delivery and a full dose delivery.
- To determine the concentration of circulating IgG after the primary series of the 2p+1 schedule, prior to boost, at 9 months of age and after the boost at 18 months of age, estimate the duration of direct protection conferred by full and fractional dose schedules and use seroepidemiology to monitor acquisition rates.
- To compare carriage prevalence at 9 and 18 months of age and IgG concentrations at 4 weeks after the primary series after full dose of PCV10 in a 3p+0 schedule, and full/ fractional doses of PCV10/13 in a 2p+1 schedule.

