Personnel assessing safety outcomes and laboratory personnel will be blinded to the type of vaccine received by each participant. The study personnel preparing and administering the vaccine will not be blind to allocation in order to administer the vaccine, but will then not participate safety assessments and will not reveal vaccination allocations to other clinic or trial personnel.

Parents will be told they will be contacted and either invited back to the clinic 7 days after vaccination to report any adverse events/ reactions or visited at home (whichever preferred) by a study fieldworker. Parents will be able to telephone study staff at any point to report possible adverse events, which will initiate an examination at the clinic, as appropriate.

CONFIDENTIAL

Fractional Dose PCV Trial Protocol Version 3.0 dated 01 May 2018

Table 2a: Time and Events Schedule – Trial arms A, B, C, D, E, F (the 2p+1 schedule)

Study visit +/-window	D0 ¹ (dose 1)	D7	D28 +/- 3d	D56 +/- 3d (dose 2)	D63 +/- 2d	D84 +/- 1wk	D228 +/- 2 wks (Boost)	D235	D256 +/- 1wk	D502 +/- 2 wks
Infant's approx. age	6wk	7wk	10wk	14wk	15wk	18wk	9m	9m	10m	18m
Clinic visit code	V1		V2	V3		V4	V5		V6	V7
Informed consent	X									
Maternal medical history and infant clinical exam	X									
HIV testing (if necessary)	X									
Inclusion and exclusion criteria checked	X									
Completion of questionnaire	X									
Blood sample ²	X					X	(X ³)		X	(X ³)
Randomization	X									
Full/ fractional dose PCV administration (IM injection)	X			X			X			
Administration of other routine vaccinations	DTwP- HepB- Hib		DTwP- HepB- Hib	DTwP- HepB-Hib; IPV			MCV1			MCV2
Observation for immediate post-vaccination reactions (within 30 minutes of vaccination)	X			X			X			
Home visit by fieldworkers - active assessment of all local injection site reactions, adverse events and severe adverse events in the 7 days following vaccination		(X)			(X)			(X)		
Active assessment of all adverse events and severe adverse events in the past 28 days at the clinic			X			X			X	
Nasopharyngeal swab for analysis of carriage prevalence							X			X
Total Blood Volume (ml) ⁴	2ml					2ml	(2ml ³)		2ml	(2ml ³)

¹ D0= Screening & enrolment; ² On vaccination visits, blood will be drawn before vaccination; ³ At randomisation, 150/300 (half) the participants in each arm will be allocated to have an additional blood draw at 9 and 18 months of age in order to assess IgG persistence; ⁴ Volume to not exceed 1ml/kg.

CONFIDENTIAL

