9.3.7 Follow-up Visits

Parents and infants will attend 6 or 7 scheduled facility visits during the trial including screening and enrolment (Table 2a and 2b).

For trial arms A-F:

- At D7, D63 and D7PB (7 days after the booster dose) i.e. 7 days after each vaccination with full or fractional doses of PCV in a 2p+1 schedule home visits will be made by fieldworkers; injection site reactions will be assessed, parents will be asked about symptoms since vaccination.
- At D28 parents will be asked to return to the health facility for routine vaccinations according to the EPI schedule (2nd dose of pentavalent vaccine and OPV), no PCV vaccine will be administered but adverse events in the 28 days since vaccination will be solicited.
- At D56, or at approximately 14 weeks of age, the infant will receive their 2nd full or fractional dose of PCV. Allocation will be indicated to the vaccinator by the participant number and a randomization log and concealed from the parent by using blinding tape over the barrel of the syringe. The location of the IM injection will be noted in source documents. At the same visit to the health facility, the third dose of pentavalent vaccine will be administered alongside IPV at different sites as per the routine immunisation schedule.
- At D84, or approximately 18 weeks of age, and at the D28PB visit, a blood sample will be drawn for immunogenicity analyses by study staff and adverse events will be solicited for the 28 days since vaccine administration.
- At D228 or approximately 9 months of age, infants will be invited to the clinic for their third and final PCV vaccination. Before vaccination, half of the participants in each arm will have an additional small blood draw at this visit, as allocated during randomisation. The vaccine will then be administered and the location of the IM injection will be noted in the source documents. The infant's first dose of measles vaccine will be administered into the upper arm as per the routine immunisation schedule. A single nasopharyngeal swab will be taken for the carriage analyses.

For trial arm G:

- At D7, D35 and D63 i.e. 7 days after each vaccination with full doses of PCV in a 3p+0 schedule home visits will be made by fieldworkers; injection site reactions will be assessed and site noted, parents will be asked about symptoms since vaccination.

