IgG GMCs in a random selection of half the participants in trial arms A-F at 9 months of age (pre-boost) and at 18 months of age (9 months post-boost) will be used to 1) estimate the duration at which GMCs remain above the threshold for protection in the first 2 years of life after a 2p+1 schedule of full or fractional doses and 2) to monitor carriage acquisition rates.

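### IgG GMCs at 9 months (pre-boost) and 18 months do not by themselves identify a carriage acquisition rate for serotypes in the infant's own vaccine; paired within-infant changes over the dose-free intervals should replace them

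*Combined protocol and SAP*

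**What the plan says.** Section 8.3 sets the objective: among other uses of the IgG measurements, the trial will "use seroepidemiology to monitor acquisition rates". The only analysis text for this is the last paragraph of section 13.2. It names the measure, "IgG GMCs in a random selection of half the participants in trial arms A-F at 9 months of age (pre-boost) and at 18 months", and gives it two purposes: estimating how long GMCs stay above the protective threshold, and "2) to monitor carriage acquisition rates".

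The sampling scheme is in section 9.3.7 and Table 2a. For arms A-F, "At D228 or approximately 9 months of age, infants will be invited to the clinic for their third and final PCV vaccination". At that visit, "Before vaccination, half of the participants in each arm will have an additional small blood draw at this visit, as allocated during randomisation". The footnote to Table 2a gives the number: "150/300 (half) the participants in each arm will be allocated to have an additional blood draw at 9 and 18 months of age". The 9- and 18-month samples therefore come from the same infants. Every infant in arms A-F is also bled at 18 weeks (D84) and one month after the booster (D256), and swabbed at 9 and 18 months.

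Section 13.2 does not mention the 18-week or 10-month samples for acquisition. No section defines a serological acquisition, a time at risk, a set of serotypes or a model. Section 13.3 leaves a detailed SAP to be finalised before database lock.

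**The concern.** An acquisition is an event in one infant over a period of time. A GMC is a group average at one age. For any serotype in the infant's vaccine, the 9-month GMC reflects the primary response, its decay and any exposure, and the 18-month GMC adds the booster response and its decay. The booster response is the quantity section 13.1 tests between doses as the primary endpoint, so it cannot be assumed equal across arms. If it differs, a dose effect on IgG could be reported as a difference in exposure.

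Nothing else in the trial supplies the missing information. Arm G, the only arm with no booster, has no blood drawn after 18 weeks (Table 2b). The two swabs give prevalence at two ages, not acquisition. At stake is a listed secondary objective that would either go unanswered or confuse immunogenicity with transmission.

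**Working it through.** The documents state no sample size, precision or power for the acquisition analysis, so there is no figure of the plan's to reproduce. The check asks which sample pairs contain a PCV dose, and whether a GMC can separate acquisition from the other causes of change.

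**1. Intervals, from the visit days and windows in Table 2a**

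| Pair | Nominal days | Range from windows | Scheduled PCV dose inside? |
|---|---|---|---|
| 9 to 18 months | 502 - 228 = 274 | 274 ± (14 + 14) = 246 to 302 | Yes, booster at D228 after the draw |
| 18 weeks to 9 months | 228 - 84 = 144 | 144 ± (7 + 14) = 123 to 165 | No |
| 10 to 18 months | 502 - 256 = 246 | 246 ± (7 + 14) = 225 to 267 | No |

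**2. What a GMC ratio contains**

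Let R be the ratio of the later GMC to the earlier one, B the fold effect of the booster (1 if none lies in the interval), d the days of decay, h the IgG half-life, p the share of infants acquiring and F their fold rise. Then

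R = B × 2^(-d/h) × F^p.

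Only R is observed. B, h and F are not in the documents, so all values used below are assumptions.

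**3. Across the booster (9 to 18 months)**

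Take h = 123 days, F = 4 and d = 246 days from the post-boost visit. For B = 5 and p = 20%: 5 × 2^(-246/123) × 4^0.2 = 5 × 0.25 × 1.32 = 1.65. In full:

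| Booster effect B | p = 0 | p = 20% | p = 40% |
|---|---|---|---|
| 5-fold | 1.25 | 1.65 | 2.18 |
| 10-fold | 2.5 | 3.3 | 4.35 |
| 20-fold | 5.0 | 6.6 | 8.71 |

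A two-fold difference between arms in B moves R as much as a difference in p of log 2 / log F. That is 0.50 for F = 4 and 0.33 for F = 8.

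**4. A GMC over an interval with no dose (10 to 18 months)**

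With B = 1, the half-life that fits a given R is h = 246 / (p × log2 F - log2 R). For R = 0.25 and F = 4:
- p = 0: 246 / 2.0 = 123 days
- p = 20%: 246 / 2.4 = 102.5 days
- p = 40%: 246 / 2.8 = 87.9 days

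The same GMC ratio fits all three. Removing the booster is not enough; the group summary also has to go.

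**5. Within-infant changes over the same interval**

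Simulated paired changes, assuming 2-fold decay, 8-fold rise on acquisition, log2 SD of the change 0.6, and a rule of at least a 2-fold rise:

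| True p | Share with rise | 95% half-width at true p, 1.96 × √(p(1-p)/150) |
|---|---|---|
| 0 | 0.0% | - |
| 10% | 9.6% | 4.8 points |
| 20% | 19.0% | 6.4 points |
| 40% | 38.2% | 7.8 points |

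These assumptions are favourable: a log2 SD of 0.6 is 0.6 × 0.301 = 0.18 on the log10 scale. With a log10 SD s of 0.35 to 0.45:
- Unexposed infants counted in error, 2-fold decay: 1 - Φ((log10 2 + log10 2)/s) = 1 - Φ(0.602/s) = 4% to 9%.
- Exposed infants detected, 5-fold rise and 4-fold decay: 1 - Φ((log10 2 - log10 1.25)/s) = 1 - Φ(0.204/s) = 28% to 33%.

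Paired changes carry information that the GMC lacks, but a fixed fold-rise rule errs in both directions.

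**The case against.** The strongest reply is that section 13.2 never says acquisition will be read from the change between 9 and 18 months. It says what the two extra bleeds are for. The other purpose in the same sentence, duration above threshold, would naturally draw on the 18-week and 10-month values as well. Section 8.3 speaks of seroepidemiology, which allows a paired individual analysis, and section 13.3 defers detail to a later SAP. This stands in part: the trial's data can support an acquisition analysis, and a direct comparison of the two GMCs is an inference. It does not rescue the named measure, because neither GMC alone, nor their ratio, identifies acquisition. Leaving room for a better analysis is not specifying one.

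Four stronger readings are tempting and are not supported:
- A reader might infer that the full-dose arms would appear to have more acquisition. The documents state no between-arm comparison of acquisition and give no fold changes across the booster. A fractional arm starting from lower pre-boost IgG could show an equal or larger rise.
- A reader might take the remark in section 5, "Persistence of high IgG concentrations could be due to the persistence of the vaccine-induced immune response and/or natural boosting through exposure", as an admission that the two causes cannot be separated. It offers both as possible explanations of another study's data and says nothing about separability.
- A reader might argue from the 6% PCV10-type carriage in section 13.2 that the signal is always below the noise. With an assumed 5-fold rise, 5^0.06 = 1.10, against a 95% CI factor of 10^(1.96 × 0.45/√150) = 1.18 for one arm's GMC. But the section's 19% for 6A and 19A gives 5^0.19 = 1.36. Both inputs are pooled point prevalences, not serotype-specific exposure over the interval, so nothing here rests on them.
- The booster objection is not universal. PCV10 contains no 6A or 19A, so, cross-reaction aside, it does not apply to those types in arms D-F. Section 11.1 leaves unclear whether they are assayed there.

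**Conclusion.** The point holds in a limited form. Followed as written, section 13.2 does not yield an acquisition rate for serotypes in the infant's own vaccine, and a dose effect on IgG could be mistaken for a difference in exposure in either direction. This conclusion rests on the visit order and on what a GMC is, not on the assumed half-life, fold rises or SDs. Those serve only to show that plausible booster differences can outweigh large differences in acquisition.

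A reader might infer that the trial cannot study acquisition at all. It can, because the scheduled samples include two paired dose-free intervals in 150 infants per arm before losses. This is a secondary use with no stated power or decision attached. It deserves correction before the SAP is finalised, and the primary endpoint is unaffected.

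**What to change.** In section 13.2, item 2, and in the SAP, replace the GMC measure with within-infant paired changes in serotype-specific IgG over the two intervals with no scheduled PCV dose: 18 weeks to 9 months (pre-boost), and 10 to 18 months.

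- Pre-specify the rise that counts as an acquisition, with an allowance for IgG decay and assay variation, before any unblinded data are seen.
- Take person-time from actual visit dates, since the windows let each interval vary by up to 21 days either way. Leave out intervals in which an infant received a PCV dose outside the trial schedule.
- Report by serotype and arm, and check against the 9- and 18-month swabs.
- State whether 6A and 19A are assayed in arms D-F, and use them there if so.
- If this is not wanted, drop the claim to monitor acquisition rates.

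The cost is protocol and SAP wording only; Table 2a already schedules all four bleeds for the subgroup. The downside is misclassification both ways: weak exposures are missed and some unexposed infants are counted. The result is therefore not a strict lower bound, and between-arm comparisons need caution if decay differs by dose.
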